3.3.1.1.4 Reports of DLT analysis

Following reports will be produced based on the dose determining safety set:

- A plot of posterior interval probabilities will be presented in the body of the CSR;
- Summary of the DLTs with onset during the evaluation period (dose escalation part only) by primary system organ class, preferred term: recommendations at the time of database lock will be included in the body of the CSR, for each dose escalation meeting (DEM), summary of recommendations will be included in Appendix 16.1.9 of the CSR;
- Listing of inferential results from the BLRM at the time of database lock, will be included in Appendix 16.1.9.

3.3.2 Phase II part

The Phase II part of the study will be conducted in adult patients enrolled in multiple indications. The analysis will be using ORR reported per RECIST v1.1 to estimate the anti-tumor activity of PDR001. A Bayesian analysis will be used to estimate the true ORR based on the observed ORR within each group, and it will be used to provide inferential summaries (e.g., mean, median,

interval probabilities) in relation to the patient population for each of the disease groups (defined in [CPDR001X2101 Amendment 8 Section 5.2]).

For a Bayesian design, a prior distribution for the parameter of interest, ORR, must be specified. For the current study, the prior clinical assumption for PDR001 in the selected patient populations is used in order to derive a minimally informative unimodal Beta prior distribution that reflects the level of uncertainty around ORR before starting the current trial (Neuenschwander et al. 2008). The prior mean ORR is conservatively set to be equal to 20% and the parameters of the minimally informative Beta prior distribution of ORR have been set up as follows:

- a/(a+b) = 0.2
- a = 0.25
- b = 1.0

At primary analysis, this prior distribution will be updated with all the data available from the patients in the FAS. See sample size estimation in [CPDR001X2101 Amendment 8 Section 10.8].

Groups 1a, 1b and 2 (NSCLC and melanoma): Estimates of the ORR for each group along with mean, median, standard deviation, and 95% credible intervals and the interval probabilities for the true ORR lying within [0%, 15%), [15%, 20%), [20%, 30%), [30%, 50%) and [50%, 100%] will be presented.

If the observed ORR is equal to or greater than 20% (i.e. \geq 12 responses (CR or PR) out of 60 patients) for NSCLC and 30% (i.e. \geq 18 responses (CR or PR) out of 60 patients) for melanoma, then this will be considered as preliminary evidence of activity of PDR001 in the respective groups.

Note that for a sample size of n = 60,

- for NSCLC (group 1a or 1b), if the observed ORR is 20%, then the posterior probability of true ORR greater than 15% is 83.7%.
- for melanoma, if the observed ORR is 30%, then the posterior probability of true ORR greater than 20% is 96.2%.

Groups 3: Estimates of the ORR for each group along with mean, median, standard deviation, and 95% credible intervals and the interval probabilities for the true ORR lying within the intervals stated below will be presented:

- [0, 10%) unacceptable efficacy
- [10, 20%) limited efficacy
- [20, 30%) moderate efficacy
- [30%, 100%] clinically relevant efficacy

Group 4 (Anaplastic thyroid cancer): Estimates of the ORR along with mean, median, standard deviation, and 95% credible intervals and the interval probabilities for the true ORR lying within the intervals stated below will be presented.

- [0, 5%) unacceptable efficacy
- [5, 10%) limited efficacy
- [10, 20%) moderate efficacy

• [20%, 100%] clinically relevant efficacy.

3.4 Efficacy evaluation

Analysis of efficacy endpoints will be performed using the FAS.

Assessment by irRC

For irRC (see [CPDR001X2101 Amendment 8 Appendix 14.2]) the key difference from RECIST v1.1 (see [CPDR001X2101 Amendment 8 Appendix 14.1]) in the assessment of these endpoints is the recommendation that irPD be confirmed at least 4 weeks after the criteria for irPD are first met. A single assessment of irPD followed by a subsequent assessment of irSD or better will be considered as a pseudo-progression, these are not considered as progression events for the purposes of analysis. Where irPD is confirmed by a second assessment, the date of the first of these two assessments is then the date of progression. For patients who have ended treatment without a valid confirmation assessment, for the purposes of analysis the single assessment of irPD will be treated as a confirmed irPD. At time of analysis there may be patients whose last adequate assessment is an unconfirmed irRC progression but who are continuing treatment. In these cases that progression will be treated as a confirmed progression for the primary analysis, and sensitivity analysis of time to event endpoints may be conducted in which the patient is censored at the time of last adequate assessment. Additional definitions and derivation rules for irRC are provided in Section 4.2.

Best overall response (BOR)

The BOR is the best response recorded from the start of the treatment until disease progression/recurrence. For RECIST v1.1 and irRC, any assessments taken before the start of any further antineoplastic therapy will be considered in the assessment of BOR in recognition that response to immunotherapy may be delayed. For both RECIST v1.1 and irRC, if any alternative antineoplastic therapy is taken while on study, any subsequent assessments will be excluded from the BOR determination.

Per RECIST v1.1, CR and PR need to be confirmed with at least two determinations of CR or PR respectively at least 4 weeks apart before progression. In order to classify overall response as SD, a patient must have at least one SD assessment (or better) > 6 weeks after start date of study treatment. In order to classify overall response as PD, a patient must have progression < 12 weeks after start date of study treatment.

Per irRC, irCR, irPR and irPD need to be confirmed with at least two determinations of irCR or irPR or irPD, respectively at least 4 weeks apart. In order to classify overall response as irSD, the patient must have at least one SD assessment (or better) > 6 weeks after start date of study treatment.

Individual lesion measurements and overall response assessments will be listed by patient and assessment date. Best overall response (BOR) per RECIST v1.1 and per irRC will be listed and tabulated.

Overall response rate (ORR) and Disease control rate (DCR)

ORR is the proportion of patients with a best overall response of CR or PR (RECIST v1.1) or of irCR or irPR (irRC). DCR is the proportion of patients with a best overall response of CR, PR, or SD (RECIST v1.1) or of irCR, irPR, or irSD (irRC).

Progression free survival (PFS)

For assessment per RECIST v1.1, PFS is the time from date of start of treatment to the date of event defined as the first documented progression or death due to any cause. If a patient has not had an event, PFS is censored at the date of last adequate tumor assessment ([CPDR001X2101 Amendment 8 Appendix 14.1.3.2.1]). For irRC, PFS is defined similarly, but with the date of event defined as the date of the first documented confirmed progression as defined in Section 4.2.3, or death due to any cause. For irRC, other censoring rules are applied as for RECIST v1.1 ([CPDR001X2101 Amendment 8 Appendix 14.1.3.2.9]).

Duration of response (DOR)

DOR applies only to patients with a BOR of confirmed CR or PR (RECIST v1.1) or of confirmed irCR or irPR (irRC). For assessment per RECIST v1.1, DOR is defined as the time from the date of the first documented response (CR or PR) to the date of first documented progression, or death due to any cause. For assessment per irRC, DOR is defined as the time from the first confirmed response (irCR or irPR), to the date of confirmed progression as defined in Section 4.2.3, or death due to any cause.

Use of alternative cancer therapy

For both RECIST v1.1 and irRC, if any alternative cancer therapy is taken other than palliative radiotherapy any subsequent assessments will be excluded from the analysis of endpoints based on tumor response assessments. If a substantial number of patients receive palliative radiotherapy, sensitivity analyses of these endpoints may be performed where assessments are also censored at the time of palliative radiotherapy.

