### 14.1.3.1 Best overall response

The best overall response is the best response recorded from the start of the treatment until disease progression/recurrence (taking as reference for PD the smallest measurements recorded since the treatment started). In general, the patient's best response assignment will depend on the achievement of both measurement and confirmation criteria.

The best overall response will usually be determined from response assessments undertaken while on treatment. However, if any assessments occur after treatment withdrawal the protocol should specifically describe if these will be included in the determination of best overall response and/or whether these additional assessments will be required for sensitivity or supportive analyses. As a default, any assessments taken more than 150 days after the last dose of study treatment will not be included in the best overall response derivation. If any alternative cancer therapy is taken while on study any subsequent assessments would ordinarily be excluded from the best overall response determination. If response assessments taken after withdrawal from study treatment and/or alternative therapy are to be included in the main endpoint determination, then this should be described and justified in the protocol.

Where a study requires confirmation of response (PR or CR), changes in tumor measurements must be confirmed by repeat assessments that should be performed not less than 4 weeks after the criteria for response are first met.

Longer intervals may also be appropriate. However, this must be clearly stated in the protocol. The main goal of confirmation of objective response is to avoid overestimating the response rate observed. In cases where confirmation of response is not feasible, it should be made clear when reporting the outcome of such studies that the responses are not confirmed.

- For non-randomized trials where response is the primary endpoint, confirmation is needed.
- For trials intended to support accelerated approval, confirmation is needed
- For all other trials, confirmation of response may be considered optional.

The best overall response for each patient is determined from the sequence of overall (lesion) responses according to the following rules:

- CR = at least two determinations of CR at least 4 weeks apart before progression where confirmation required or one determination of CR prior to progression where confirmation not required

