- PR = at least two determinations of PR or better at least 4 weeks apart before progression (and not qualifying for a CR) where confirmation required or one determination of PR prior to progression where confirmation not required
- SD = at least one SD assessment (or better) > 6 weeks after randomization/start of treatment (and not qualifying for CR or PR).
- PD = progression ≤ 12 weeks after randomization/ start of treatment (and not qualifying for CR, PR or SD).
- UNK = all other cases (i.e. not qualifying for confirmed CR or PR and without SD after more than 6 weeks or early progression within the first 12 weeks)

Overall lesion responses of CR must stay the same until progression sets in, with the exception of a UNK status. A patient who had a CR cannot subsequently have a lower status other than a

PD, e.g. PR or SD, as this would imply a progression based on one or more lesions reappearing, in which case the status would become a PD.

Once an overall lesion response of PR is observed (which may have to be a confirmed PR depending on the study) this assignment must stay the same or improve over time until progression sets in, with the exception of an UNK status. However, in studies where confirmation of response is required, if a patient has a single PR ( $\geq 30\%$  reduction of tumor burden compared to baseline) at one assessment, followed by a  $< 30\%$  reduction from baseline at the next assessment (but not  $\geq 20\%$  increase from previous smallest sum), the objective status at that assessment should be SD. Once a confirmed PR was seen, the overall lesion response should be considered PR (or UNK) until progression is documented or the lesions totally disappear in which case a CR assignment is applicable. In studies where confirmation of response is not required after a single PR the overall lesion response should still be considered PR (or UNK) until progression is documented or the lesion totally disappears in which case a CR assignment is applicable.

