Example: In a case where confirmation of response is required the sum of lesion diameters is 200 mm at baseline and then 140 mm - 150 mm - 140 mm - 160 mm - 160 mm at the subsequent visits. Assuming that non-target lesions did not progress, the overall lesion response would be PR - SD - PR - PR - PR. The second assessment with 140 mm confirms the PR for this patient. All subsequent assessments are considered PR even if tumor measurements decrease only by 20% compared to baseline (200 mm to 160 mm) at the following assessments.

If the patient progressed but continues study treatment, further assessments are not considered for the determination of best overall response.

Note: these cases may be described as a separate finding in the CSR but not included in the overall response or disease control rates.

The best overall response for a patient is always calculated, based on the sequence of overall lesion responses. However, the overall lesion response at a given assessment may be provided from different sources:

- Investigator overall lesion response
- Central Blinded Review overall lesion response
- Novartis calculated overall lesion response (based on measurements from either Investigator or Central Review)

The primary analysis of the best overall response will be based on the sequence of investigator overall lesion responses.

Based on the patients' best overall response during the study, the following rates are then calculated:

**Overall response rate (ORR)** is the proportion of patients with a best overall response of CR or PR. This is also referred to as 'Objective response rate' in some protocols or publications.

**Disease control rate (DCR)** is the proportion of patients with a best overall response of CR or PR or SD.

Another approach is to summarize the progression rate at a certain time point after baseline. In this case, the following definition is used:

**Early progression rate (EPR)** is the proportion of patients with progressive disease within 8 weeks of the start of treatment.

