#### **14.2.4 Definitions of response categories and evaluation of overall lesion response**

In irRC, the overall response is primarily based on target lesions (baseline and new measurable lesions). The non-target lesions only contribute to define irCR, and irPD in the case of unequivocal progression, as shown below in [Table 14-6](#).

Like in RECIST 1.1, irCR and irPR must be confirmed at a new assessment after at least 4 weeks. Unlike RECIST 1.1, irPD also requires confirmation at a new assessment after at least 4 weeks.

The response categories are defined as follows:

- Immune related Complete Response (irCR): Disappearance of all non-nodal target lesions and non-target lesions in two consecutive observations not less than 4 weeks apart. In addition, any pathological lymph nodes assigned as target lesions must have a reduction in short axis to < 10 mm. (Sum of diameters may be greater than zero at the time of CR, if nodal lesions are included as target lesions).
- Immune related Partial Response (irPR): At least a 30% decrease in the sum of diameters of all target lesions including new target lesions in two consecutive observations not less than 4 weeks apart, taking as reference the baseline sum of diameters.
- Immune related Progressive Disease (irPD): At least a 20% increase in the sum of diameters of all measured target lesions including new measurable lesions. The irPD must be confirmed in a second evaluation not less than 4 weeks later, taking as reference the smallest sum of diameter of all target lesions recorded at or after baseline (nadir). In addition to the relative increase of 20%, the sum must also demonstrate an absolute increase of at least 5 mm. Worsening of non-target lesions (existing or new) only indicate PD when there is unequivocal evidence of progression, confirmed in a second evaluation not less than 4 weeks later.
- Immune related Stable Disease (irSD): Neither a sufficient shrinkage to qualify for irPR or irCR, nor an increase in lesions which would qualify for irPD.
- Unknown (UNK): Progression has not been documented and one or more target lesions or new measurable lesions observed at earlier assessment have not been/could not be assessed, or have been assessed using a method significantly different from baseline (target lesions) or assessment of first occurrence (for new measurable lesions) that prevents reasonable comparison to the prior assessments.

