4.2.3 Best overall response

Assessment of BOR will be based on all assessments up to and including the first assessment of irPD (cPD1, cPD2, or uPD). Assessments made after start of new anti-cancer therapy, will be excluded.

BOR will be defined with the following hierarchy:

irCR	Two consecutive determinations of irCR ≥28 days (4 weeks) apart
	Non-consecutive assessments of irCR may also result in BOR of irCR if all intervening assessments are irUNK
irPR	•
IIPK	Two determinations of irPR (or better) \geq 28 days (4 weeks) apart
	The two determinations of irPR (or better) may be separated by one or more
	assessments of irSD, but may not be separated by an assessment of irPD
irSD	At least one irSD assessment (or better) > 42 days (6 weeks) after first treatment
irPD	Event flagged as cPD1, cPD2 or uPD ≤ 84 days (12 weeks) after first treatment
irUNK	All other cases

4.2.4 Time to event analyses:

4.2.4.1 **Progression events**

PDs flagged as pPD are not included in time to event analyses.

SAP final CSR 24-Jul-2020 (11:48) CPDR001X2101

Subjects are classified as follows:

	0	No event (censored) Confirmed PD (cPD1 or cPD2)	
	1		
Ī	2	Unconfirmed PD (uPD)	

For the primary analysis of time to event endpoints, both confirmed and unconfirmed progression will be included as progression events with date of progression being the date of the assessment flagged as cPD1, cPD2 or uPD according to the algorithm defined in Section 4.2.2.

A sensitivity analysis of time to event endpoints may be conducted in which subjects with unconfirmed PD are treated as censored, with date of last adequate assessment = visit date for assessment flagged uPD.

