4.2.4.4 Duration of response

Duration of response is defined as a time interval between the first date of confirmed PR/CR and the date of progression as defined in Section 4.2.4.1, or death due to any cause. Intervening assessments of pPD are excluded from the assessment.

Date of confirmed response

Response (irPR or irCR) should be confirmed by a second assessment no less than 4 weeks after the first assessment showing response. Date of response is then the date of the first of these two assessments. For confirmation of irCR the two assessments must be consecutive (intervening assessments of irUNK are permissible). For confirmation of irPR the two assessments do not need to be consecutive, but must not be separated by a pseudo-progression event.

The table below shows a hypothetical data scenarios with programming instructions.

Sequence of assessments	Instructions	
1 irPR	The first PR (assessment 1) is followed by a pseudo-progression	
2 irPD	(assessment 2) and is therefore not confirmed	
3 irPR	Subsequently the Subject has a irPR (assessment 3) which is	
4 irPR	confirmed at the following assessment (assessment 4)	
	The BOR for this Subject is irPR, with date of confirmed irPR equal to the date of assessment 3	

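### Read literally, SAP 3.4 confirms PR and irPR by different rules from protocol 14.1.3.1 and SAP 4.2.3, and protocol 14.2.4 gives another rule for irPR

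*SAP*

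**What the plan says.** Confirmation is required here. Protocol 14.1.3.1 states: "For non-randomized trials where response is the primary endpoint, confirmation is needed". ORR counts patients by confirmed best overall response, so the confirmation rule decides who is a responder.

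**RECIST 1.1 (primary ORR)**

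- Protocol 14.1.3.1: "PR = at least two determinations of PR or better at least 4 weeks apart before progression (and not qualifying for a CR").
- The same section works through a PR, SD, PR sequence: "The second assessment with 140 mm confirms the PR for this patient". Under RECIST the two assessments therefore need not be adjacent.
- SAP 3.4: "CR and PR need to be confirmed with at least two determinations of CR or PR respectively at least 4 weeks apart before progression".

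**irRC (secondary ORR and DOR)**

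- Protocol 14.2.4 defines irPR by a decrease of at least 30% in the sum of diameters, "including new target lesions in two consecutive observations not less than 4 weeks apart".
- SAP 3.4: irCR, irPR and irPD "need to be confirmed with at least two determinations of irCR or irPR or irPD, respectively". It says nothing about what may lie between the two.
- SAP 4.2.3: "The two determinations of irPR (or better) may be separated by one or more" irSD assessments, but not by irPD.
- SAP 4.2.4.4: "For confirmation of irPR the two assessments do not need to be consecutive", provided no pseudo-progression falls between them.

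Protocol 10.5.2 places the RECIST definitions of the secondary endpoints in Appendix 14.1 and leaves the irRC definitions to the analysis plan (RAP). SAP 3.4 points to both protocol appendices and to its own Section 4.2 for additional irRC rules.

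**The concern.** The word *respectively* in SAP 3.4 pairs CR with CR and PR with PR. Programmed as written, one PR followed by one CR confirms neither. The SAP's own clause for SD, which needs one assessment of SD or better more than 6 weeks after treatment start, then makes that patient SD. A later PR cannot repair this, because protocol 14.1.3.1 allows only CR, UNK or PD after a CR. The patients lost are those whose response deepened. They leave the numerator of the Phase II primary endpoint and the set analysed for DOR.

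For irRC, three current texts give three rules, and each pair of rules disagrees on at least one plausible sequence. That affects the secondary irRC ORR, membership of the irRC DOR set and, for some patients, the date from which DOR runs.

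**Working it through.** **1. The plan's own figures.** Inputs: prior Beta(0.25, 1.0) and n = 60 with activity at 12 (NSCLC) or 18 (melanoma) responders, from protocol 10.4.2; n = 40 with efficacy at an ORR of 20%, that is 8 responders (TNBC), from protocol 10.8. With X ~ Binomial(n, p), P(X ≥ r) reproduces all 18 cells of Table 10-2. For NSCLC it gives 1.46%, 18.06%, 55.14%, 85.24%, 97.05% and 99.97%. The posterior Beta(0.25 + r, 1 + n − r) gives P(ORR>15%) = 83.71% at 12/60 and P(ORR>20%) = 96.21% at 18/60, matching the stated 83.7% and 96.2%. No printed figure is wrong.

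**2. RECIST rules applied to the same patients** (scans 8 weeks apart):

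| Sequence | Protocol 14.1.3.1 | SAP 3.4, literal |
|---|---|---|
| PR, PR, PD | PR | PR |
| PR, SD, PR | PR | PR |
| PR, CR, CR | CR | CR |
| PR, CR, PD | PR | SD |
| SD, PR, CR (last scan) | PR | SD |

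The rules part only where the qualifying responses are exactly one PR and one CR.

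**3. irRC rules applied to the same patients** (a CR scan is taken also to meet the 30% decrease):

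| Sequence | Protocol 14.2.4 | SAP 3.4, literal | SAP 4.2.3 |
|---|---|---|---|
| irPR, irPR | irPR | irPR | irPR |
| irPR, irSD, irPR | not a responder | irPR | irPR |
| irPR, irCR | irPR | not a responder | irPR |
| irPR, pseudo-progression, irPR | not a responder | irPR | not a responder |

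**4. Start of DOR.** For irPR, irSD, irPR, irPR, SAP 4.2.4.4 dates the response at scan 1. The consecutive rule is first met by scans 3 and 4, so the response dates from scan 3. On the 8-week schedule that is 2 × 8 = 16 weeks later.

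**5. One lost responder at the RECIST threshold.** One patient moves ORR by 1/60 = 1.7 points or 1/40 = 2.5 points.

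| Group | Change | Observed ORR | Posterior probability |
|---|---|---|---|
| NSCLC | 12/60 to 11/60 | 20% to 18.3% | P(ORR>15%): 83.7% to 74.0% |
| Melanoma | 18/60 to 17/60 | 30% to 28.3% | P(ORR>20%): 96.2% to 93.1% |
| TNBC | 8/40 to 7/40 | 20% to 17.5% | P(ORR>10%): 96.6% to 91.7% |

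Each change crosses the stated threshold. With true ORR at its 20% reference value, the chance of landing exactly on the threshold is 12.8% for 12/60 and 15.6% for 8/40. These are not chances of a reversal, which also needs an affected patient among the responders.

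**6. Range for the unknown share.** The documents do not say what share f of responders have only one PR and one CR. Assume f = 2%, 5% or 10% and compute P(X ≥ r) with response probability p(1 − f):

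| Group, true ORR | f = 0 | 2% | 5% | 10% |
|---|---|---|---|---|
| NSCLC, 20% | 55.1% | 52.0% | 47.3% | 39.4% |
| NSCLC, 30% | 97.1% | 96.3% | 95.0% | 91.8% |
| Melanoma, 40% | 95.9% | 94.6% | 92.3% | 86.6% |
| TNBC, 30% | 94.5% | 93.5% | 91.8% | 88.3% |

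**The case against.** The strongest reply on RECIST is that the SAP sentence is a one-line summary. The SAP says it is based on Protocol Amendment 8. The sentence opens by invoking RECIST v1.1, SAP 3.4 points to Appendix 14.1, and the full rule is there. A CR scan normally meets the PR size criterion too. Nothing suggests that the SAP set out to replace the protocol rule. This largely stands as to intent. It does not settle the text. The SAP describes itself as the detailed methodology for the study report, SAP 4.2.3 does write *or better* for irPR, and no sentence says which document prevails.

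On irRC, the reply is that the protocol hands the definitions to the analysis plan and SAP 3.4 directs the reader to Section 4.2, where 4.2.3 and 4.2.4.4 agree with each other. That also stands as a strong indication that Section 4.2 governs. But SAP 3.4 still cites protocol Appendix 14.2, where the consecutive requirement remains, and its own summary sentence differs from 4.2.3.

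A reader might infer that DCR also moves. It does not: a PR at the first scan (week 8 ± 1) already meets the SD condition of more than 6 weeks, so a reclassified patient becomes SD or irSD and still counts. A reader might also carry the threshold figures over to irRC. They do not transfer, because irRC ORR is only summarised with a 90% exact interval and has no decision rule.

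**Conclusion.** The texts conflict, and followed literally SAP 3.4 gives a wrong result for identifiable patients.

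- **RECIST:** the group is narrow, with exactly one PR followed by one CR and no second of either. The likely cause is loose wording. The consequence is loss from ORR and DOR. An activity call reverses only if the count sits on the threshold and at least one of those responders is affected.
- **irRC:** the conflict over consecutive observations does not depend on how one word is read, but it concerns a secondary endpoint whose definition the protocol delegates.

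It would go too far to conclude that the primary ORR as a whole turns on which sentence is programmed. PR then PR, PR with SD between, and a confirmed CR are classified alike under both RECIST texts. The number of affected patients is not in the documents, so the 2% to 10% range is an assumption and the effect may be small. The point is worth correcting because the wrong result falls on deep responders and the remedy is simple.

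**What to change.** Change the SAP only.

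1. In 3.4, for RECIST, state the two categories separately: CR needs at least two CR assessments, and PR needs at least two assessments showing PR or better. In both cases they must be at least 4 weeks apart and before progression. Remove *respectively*.
2. In 3.4, for irRC, replace the confirmation sentence with a reference to Section 4.2.3.
3. State that for irPR, SAP 4.2.3 and 4.2.4.4 prevail over the consecutive-observations wording in protocol 14.2.4.

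The cost is a few lines, made by SAP amendment before database lock or by addendum after it, as the SAP introduction provides. No new data are needed. Because protocol 10.5.2 already leaves irRC definitions to the analysis plan, no protocol amendment is needed.
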